6.2 Handling of Dropouts

A patient who discontinues study participation prematurely for any reason after randomization is defined as a "dropout". Patients who drop out will not be replaced.

A patient who, for any reason (e.g., failure to satisfy the selection criteria), terminates the study before the time point used for the definition of "dropout" in this study is regarded a screen failure.

In all cases, the reason for withdrawal must be entered in the eCRF and in the patient's medical records.

6.3 Handling of Patients from Site 065-S

Patients included at site 065-S will be presented in all listings and in specific tables of interest.

6.4 Handling of Rescreened Patients

Patients who are rescreened will be presented once in summary tables utilizing the most recent subject identifier. Both new and old subject identifier will be presented in listings.

6.5 Handling of Missing Data

In order to achieve the goal of a well conducted clinical trial according to International Council on Harmonization Good Clinical Practice, every effort should be made to collect all data (i.e., if a patient misses a scheduled assessment, the site personnel should contact the patient and request him/her to come to the clinic for the visit). However, despite best efforts, it may be inevitable that missing or incomplete data are reported. All missing or partial data will be presented in the patient data listings, as they were recorded on the eCRF.

6.5.1 Safety Variables

Incomplete adverse event start or stop dates and concomitant medication start or stop dates will be imputed to determine treatment-emergent AE and concomitant medication as described in **Table 3**. Missing or partial dates will be presented in the patient data listings as they were recorded on the CRFs.

Statistical Analysis Plan

Sponsor Name: Poxel
 Sponsor Protocol ID: PXL065-003

Table 3 - Imputation Rules for Incomplete Dates for AE and Concomitant Medication

	Missing	Scenario	Imputation
Start date (AE, concomitant medication)	Day	Event month&year < month&year of first dose	last day of the month
		Event month&year = month&year of first dose	first dose date
		Event month&year > month&year of first dose	first day of the month
	Day / Month	Event year < year of first dose	December 31
		Event year = year of first dose	first dose date
		Event year > year of first dose	January 01
	Complete missing		AE: first dose date Conmed: no imputation
Stop date (AE, concomitant medication)	Day	Event month&year < month&year of last known assessment date (LKAD)	last day of the month
		Event month&year = month&year of LKAD	date of LKAD
		Event month&year > month&year of LKAD	no imputation
	Day / Month	Event year < year of LKAD	December 31
		Event year = year of LKAD	date of LKAD
		Event year > year of LKAD	no imputation
	Complete missing		date of LKAD

Note: If first dose date is missing, use randomization date for the imputation.

If the imputed start date is after the stop date, the start date will be imputed to equal the stop date.

If the imputed stop date is before the start date, the stop date will be imputed to equal the start date.

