### 5.1 Inclusion Criteria

1. Capable of providing written informed consent. Male or female patients must have given written informed consent before any study-related activities are carried out
2. Age:  $\geq 18$  to  $\leq 75$  years at informed consent signature
3. Body mass index (BMI)  $\leq 50 \text{ kg/m}^2$  during Screening Period
4. Estimated glomerular filtration rate (eGFR)  $\geq 45 \text{ mL/min/1.73m}^2$  during Screening Period calculated by the Chronic Kidney Disease – Epidemiology collaboration (CKD-EPI) formulae
5. Either T2DM or non-T2DM patients (after 50% non-T2DM patients have been randomized, only T2DM patients will be eligible).

If T2DM patients:

- a. Glycated hemoglobin (HbA1c)  $\leq 9.5\%$  during Screening Period
- b. If treatment-naïve: patients must be diagnosed and under diet and exercise for the last 6 months prior to Randomization Visit (V1)
- c. If currently treated: patients must be on stable mono- or bi-therapy (i.e. same doses and same drug(s)).

Permitted antidiabetic drugs are:

- Metformin, sitagliptin, alogliptin: stable for at least 3 months prior to Randomization Visit (V1)
- Empagliflozin, canagliflozin, dapagliflozin: stable for at least 6 months prior to Randomization Visit (V1)

All other antidiabetic drugs are not allowed

6. Liver fat content (LFC)  $\geq 8\%$  measured with magnetic resonance imaging-proton density fat fraction (MRI-PDFF) during the Screening Period
7. Noncirrhotic, biopsy-proven NASH patients with:
  - Histological evidence of NASH based on liver biopsy with a NonAlcoholic Fatty Liver Disease (NAFLD) Activity Score (NAS)  $\geq 4$  (at least 1 point in each histological feature: steatosis, lobular inflammation and hepatocellular ballooning)
  - Histological evidence of liver fibrosis defined as NASH CRN System fibrosis score F1, F2 or F3. F1 patients must have at least one of these risk factors: T2DM, BMI  $\geq 30 \text{ kg/m}^2$ , and/ or ALT  $> 1.5 \times \text{ULN}$ . After 35% of patients with a fibrosis score of F1 have been randomized only patients with F2 and F3 will be eligible
8. Qualifying liver biopsy must be obtained within 6 months prior to Randomization Visit (V1). If there is no available liver biopsy within this period, a liver biopsy must be performed during the Screening Period

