6.5.3 Type 2 Diabetes Diagnosis

Partial dates for diagnosis of type 2 diabetes will be handled in the following way,

- Missing day only: Impute using the last day of the month
- Missing day and month: Impute using the last day of the year

Statistical Analysis Plan

Sponsor Name: Poxel
Sponsor Protocol ID: PXL065-003

If the imputed date goes beyond the informed consent date, then impute to the date of informed consent.

7. Statistical Methods

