7.4.2 Previous and Concomitant Medications

Medications received prior to or concomitantly with IMP treatment will be coded by using the World Health Organization (WHO) Drug Dictionary [Version WHODrug Mar 2020], Anatomical Therapeutic Chemical (ATC) Classification codes.

Prior medications and concomitant medications are defined as follows:

Prior medications are defined as medications taken within 28 days prior to informed consent form (ICF) signature and stopped before or on ICF signature date.

Concomitant medications are medications that are ongoing before and continue after the ICF signature

New medications are medications that are prescribed during the study (Starting after ICF signature).

If a medication cannot be classed as prior or concomitant after applying imputation rules for missing/incomplete dates, it will be classed as concomitant.

Prior, concomitant and new medications will be listed for the Safety set with site 065-S: and summarized separately for the Safety set, with summary tables displayed by treatment group.

The number and percentage of patients using each medication will be displayed together with the number and percentage of patients using at least one medication within each indication, WHO ATC-Level 1, WHO ATC-Level 3, therapeutic class, and PT. The number and percentage of patients using medication for each different indication will also be displayed.

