7.8 Interim Analysis

Not applicable

8. Changes in Planned Analysis

- Changes from SAP v2.0 (12May2022) to SAP Final v3.0 (12Aug2022):
 - Treatment exposure end date coded as 23rd December 2021 per NTF for patients that did not complete the study at site 065-S
 - PPS description updated following the BDRM
 - Removal of analyses utilizing multiple imputation on the PPS
 - Multiple imputation method updated to consider a minimum and maximum value
 - CMH and logistic regression analysis removed for “Patients without any MRI assessments on treatment being classified as non-responders”
 - Analysis on biopsy exploratory endpoints updated to consider only patients with Week 36 assessments
 - EoS Visit end date removed for derivation of new medications
- Changes from SAP v1.0 (03Dec2020) to SAP Final v2.0 (17May2022):
 - Updates per issue with site 065-S
 - Section 1 updated to mention note to file for the handling of site 065-S
 - Analysis populations section includes description of the issue with site 065-S and the handling of the analysis sets
 - Section 7 updated to specify which analyses are done with and without site 065-S
 - Updates to disposition table
 - Additional MMRM analysis for weight (kg)
 - Section 7.6.2.5 added for new subgroup analyses on secondary endpoints
 - Updates per dry run 1
 - Rescreened patients excluded from screened set
 - Demographics - BMI and Weight at baseline rather than randomization
 - Updates to TEAE overall table
 - Inclusion of urine pregnancy summary and listing
 - Inclusion of immediate pregnancy reporting listing
 - Updates per protocol amendment 5
 - Additional section for handling of rescreened patients
 - Removal of albuminuria/creatininuria ratio
 - Updates to prohibited medication
 - Imputation rules added for type 2 diabetes diagnosis
 - PK analysis is now being reported separately

Statistical Analysis Plan

Sponsor Name: Poxel
Sponsor Protocol ID: PXL065-003

- References to Covance updated to Labcorp/Labcorp Drug Development
- Approval of SAP version 1.0 dated 03Dec2020

9. Data Issues

Issues concerning site 065-S have been documented in Section 5 and in a note to file.

10. References

- 1 ICH. *Statistical Principles for Clinical Trials*, Guideline E9, 1998. Available at <http://www.emea.eu.int/pdfs/human/ich/036396en.pdf>
- 2 CPMP. *Points to Consider on Missing Data*. EMEA: London, 2001. Available at <http://www.emea.eu.int/pdfs/human/ewp/177699EN.pdf>

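### SAP Table 3 dates partial medication starts from first dose while medications are classified from consent, so some drugs begun before consent can be tabulated as new

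*SAP*

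**What the plan says.** SAP 6.5.1 has one table for incomplete dates: AE and "concomitant medication start or stop dates will be imputed to determine treatment-emergent AE and concomitant medication as described in" Table 3. For start dates the reference point is always first dose:

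- Day and month missing, "Event year = year of first dose": the start becomes the first dose date.
- Day and month missing, "Event year < year of first dose": the start becomes 31 December of the recorded year.
- Only the day missing, "Event month&year < month&year of first dose": the start becomes the last day of the recorded month.
- Wholly missing medication start: not imputed.

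The consent date does not appear in Table 3. A footnote sets the start equal to the stop date when the imputed start would fall after it.

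SAP 7.4.2 classifies by consent. Concomitant drugs were already in use at consent and continued. For the third class it says: "New medications are medications that are prescribed during the study (Starting after ICF signature"). Protocol 6.4 uses the same reference point. A fallback in 7.4.2 sends a drug to concomitant if, after imputation, it can be classed as neither prior nor concomitant.

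For partial diabetes diagnosis dates, SAP 6.5.3 adds a limit: "If the imputed date goes beyond the informed consent date, then impute to the date of informed consent". Table 3 has no such limit for medications.

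**The concern.** First dose is the right reference for deciding whether an adverse event is treatment-emergent. It is the wrong one for deciding whether a drug was in use at consent, because first dose follows consent by the length of screening. Using it for both purposes can push a background drug past consent and turn it into an apparent addition.

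This can contradict the trial's own eligibility rules. Protocol 5.1 requires "Metformin, sitagliptin, alogliptin: stable for at least 3 months prior to Randomization Visit (V1"), and a longer period for the permitted SGLT2 inhibitors. Protocol 6.4 stresses that antidiabetic and lipid-lowering drugs should stay unchanged because they may affect the efficacy endpoints. A by-arm table of new medications is where a reader would look for added co-treatment, and some of its entries could be products of the imputation rule.

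**Working it through.** **Inputs.** First dose is on the day of V1 (protocol 6.2.1). Consent is at most 8 weeks (56 days) before V1 (protocol 4.1), or 12 weeks (84 days) under the COVID-19 memo (SAP 2.4). Stability before V1 is at least 3 months (about 91 days) for metformin, sitagliptin and alogliptin, and at least 6 months (about 182 days) for the SGLT2 inhibitors (protocol 5.1).

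**Rule.** A drug is new if its imputed start is later than the consent date. The illustrative dates below have gaps of 49 and 51 days, both within 8 weeks.

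| Case | Consent | First dose | Recorded start (true start) | Table 3 gives | Class |
|---|---|---|---|---|---|
| a | 10 Jun 2021 | 29 Jul 2021 | 2021 (Feb 2021) | 29 Jul 2021 | new |
| b | 20 Nov 2020 | 10 Jan 2021 | 2020 (Mar 2020) | 31 Dec 2020 | new |
| c | 10 Jun 2021 | 29 Jul 2021 | Jun 2021 (3 Jun) | 30 Jun 2021 | new |
| d | 10 Jun 2021 | 29 Jul 2021 | Apr 2021 (20 Apr) | 30 Apr 2021 | concomitant |
| e | 10 Jun 2021 | 29 Jul 2021 | 2018 (May 2018) | 31 Dec 2018 | concomitant |

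If the drug in case (a) is metformin, eligibility puts its start no later than 29 April 2021. That is 91 − 49 = 42 days before consent, yet it is classed as new.

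**How often.** The documents do not give start dates, so this part rests on assumptions: first dose evenly spread over 1 October 2020 to 30 September 2021; a fixed gap from consent to first dose; true start evenly spread from the stability limit back to 730 days before first dose; drug ongoing. This gives 365 × 640 = 233,600 combinations for the 3-month rule and 365 × 549 = 200,385 for the 6-month rule. Share moved past consent:

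| Gap (days) | At least 3 months, year only | At least 6 months, year only | At least 3 months, only day missing |
|---|---|---|---|
| 28 | 45,570 / 233,600 = 19.5% | 22,274 / 200,385 = 11.1% | 0% |
| 56 | 54,432 / 233,600 = 23.3% | 28,588 / 200,385 = 14.3% | 0% |
| 70 | 59,157 / 233,600 = 25.3% | 32,039 / 200,385 = 16.0% | 480 / 233,600 = 0.2% |
| 84 | 64,078 / 233,600 = 27.4% | 35,686 / 200,385 = 17.8% | 3,154 / 233,600 = 1.4% |

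The zeros follow directly. With a 56-day gap, a 3-month-stable drug began at least 91 − 56 = 35 days before consent, so the end of its start month always precedes consent. For the 6-month rule, no day-only-missing date moves at any of these gaps.

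**By type of date, all drugs truly begun before consent:**

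- Year-only, year of first dose: 100% moved.
- Year-only, consent year, when screening crosses 1 January: 96–99%. The exception is consent on 31 December.
- Month and year, consent month: 5,020 / 5,373 = 93%. The exception is mainly consent on the last day of a month.
- Year before the consent year, or month before the consent month: 0%.

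**Sensitivity to the look-back.** A separate simulation, with gaps of 28–56 days, gives 49%, 21% and 8% of year-only dates moved for look-backs of 12, 24 and 60 months (3-month rule), and 36%, 13% and 4% (6-month rule). The longer a drug has been in use, the less often it is moved.

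**With a cap at the consent date**, no pre-consent drug has an imputed start after consent: 0% in every scenario.

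**The case against.** The strongest reply is the fallback in SAP 7.4.2. If it is limited to drugs with incomplete dates, the metformin in case (a) returns to concomitant, which is correct. But then every truly new drug with a partial date goes to concomitant as well. Read literally, no new drug is prior or concomitant, so the new class would be empty. Read narrowly, the fallback covers only drugs still unclassifiable after imputation, and case (a) has been made classifiable. The wording is open, so it does not clearly cure the problem. It can also be said that a pre-study drug was not prescribed during the study, but the definition's own parenthesis makes the start date the test.

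The other limits stand, and they rule out several stronger inferences:

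- A reader might infer that background drugs in general become new. The working shows otherwise. Drugs stopped on or before consent are also protected, by the Table 3 footnote on stop dates.
- A reader might infer that the stability rules always prove a pre-consent start. The 3-month rule does so within 8 or 12 weeks of screening, but protocol 4.1 also allows exceptional extensions limited only by the MRI-to-V1 interval. For lipid-lowering drugs, protocol 5.2 asks only for no change in the month before V1, so a start during screening is possible.
- A reader might infer that the new-medication table is the only view of added co-treatment. It is not: listings show dates as recorded (SAP 6.5.1), and important deviations leading to per-protocol exclusion are summarized by arm (SAP 7.3).
- A reader might object that the new class mixes screening, treatment and follow-up, the more so since SAP Section 8 records "EoS Visit end date removed for derivation of new medications". Protocol 6.4 also defines a single class, and follow-up is two weeks, so splitting it is a preference.

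**Conclusion.** The two sections use different reference dates, and the mismatch produces wrong classes in identifiable cases. That much follows from the text alone. The size does not: the 20–27% and 11–18% figures apply only to year-only starts of drugs covered by the stability rules, under an assumed 24-month even spread, and the documents do not say how many dates are year-only.

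The reach is modest. Only the descriptive prior, concomitant and new medication tables change. No efficacy analysis, treatment-emergence definition or stated per-protocol rule uses this classification. With about 30 patients randomized per arm, one patient wrongly counted moves a row by 1/30, about 3 percentage points, or slightly more in a Safety Set that excludes one site. Nothing in the documents suggests that the error would favour one arm. It is worth correcting because it can make stable background treatment look newly added, and the correction is small.

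**What to change.** In SAP 6.5.1, keep Table 3 as it is for adverse events and give medications their own start-date rule. Either compare partial medication starts with consent, or apply Table 3 and then cap the result at the consent date, as in 6.5.3. Apply this when the recorded partial date is compatible with a start on or before consent and the drug is not known to have begun on study. That knowledge should come from a prior/ongoing item in the eCRF or, if there is none, from a data query.

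In SAP 7.4.2, state that a start equal to the consent date counts as concomitant if the drug is ongoing. Reword the fallback so that it applies only to a medication that cannot be placed in any of the three classes.

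The cost is a few lines of text and a small programming change, plus queries if the eCRF has no suitable item; the eCRF was not available to check. One small downside remains: a truly new drug with a year-only date and no other information would be classed as concomitant. Showing new medications separately for screening, treatment and post-treatment is optional.

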6.5.2 Laboratory Values

For laboratory values below the lower limit of quantification (LLOQ) like "<xxx" or " \leq xxx", or above the upper limit of quantification (ULOQ) like ">xxx" or " \geq xxx", LLOQ or ULOQ (xxx) will be used for calculation of descriptive statistics. The original laboratory values ("<xxx", " \leq xxx", ">xxx" or " \geq xxx") are presented in the listing.

6.5.3 Type 2 Diabetes Diagnosis

Partial dates for diagnosis of type 2 diabetes will be handled in the following way,

- Missing day only: Impute using the last day of the month
- Missing day and month: Impute using the last day of the year

Statistical Analysis Plan

Sponsor Name: Poxel
Sponsor Protocol ID: PXL065-003

If the imputed date goes beyond the informed consent date, then impute to the date of informed consent.

7. Statistical Methods

7.1 General Principles

All data processing, summarization and analyses will be performed using SAS Environment / Version 9.4 (or later) of the SAS® statistical software package.

The following principles will be applied to all tables, figures and listings (TFLs) unless otherwise stated:

Principle	Value
Significant tests	Two-sided and use a 5% significance level for main effect
Treatment group labels and order presented	PXL065 7.5mg QD PXL065 15 mg QD PXL065 22.5mg QD Placebo
Visit labels presented	Tables and Figures: Week XX Listings: Screening Randomization (V1) Week 3 (V2) Week 6 (V3) ... Week 36 (V8-EoT) End of Study (V9-EoS) Early termination Unscheduled
Tables	Data in summary tables presented by treatment group, assessment (where applicable) and analysis visit (where applicable).
Listings	All data collected presented by treatment group, patient, nominal visit, Date unless otherwise specified.
Descriptive summary statistics for continuous variables	Number of patients/observations (N) Mean SD standard error of the mean (SEM), median interquartile range (25 th percentile, 75 th percentile) (Q1, Q3) minimum and maximum
Descriptive summary statistics for categorical variables	Frequency counts and percentages: n (%)
Denominator for percentages	Number of patients in the analysis population, unless stated otherwise in table shell(s).
Include "Missing" as category	Yes, when the number missing is greater than zero for at least one treatment group.

Statistical Analysis Plan

Sponsor Name: Poxel
Sponsor Protocol ID: PXL065-003

Principle	Value
Display for 0 percentages	Leave blank
Display to one more decimal place than collected value	Mean SEM Mean Difference Median Interquartile range (Q1, Q3)
Display to 2 more decimal places than collected value	SD Confidence Intervals (CI)
Limit of precision for displays	3 decimal places
Date Format for the presentation in the listings	DDMMYYYY

The baseline value is defined as last scheduled or unscheduled value collected prior to the first dose of IMP treatment, scheduled on Randomization Visit (V1). Assessments carried out on day of first treatment administration are considered to have taken place before the IMP administration, if the corresponding times have not been recorded.

7.2 Patient Disposition and Data Sets Analyzed

Patient disposition will be listed and summarized (for screened set and screened set with site 065-S) by treatment group and overall and will include the number and percentage of patients:

- Screened;
 - Discontinued during screening period;
 - Discontinued during screening period due to COVID-19
- Randomized into double-blind period
 - Randomized but did not receive a dose of IMP
 - Randomized and received at least one dose of IMP;
 - Randomized but discontinued IMP/Study;
 - Patients whose primary reason for withdrawal was due to COVID-19 pandemic circumstances;
 - Patients who had study treatment temporarily interrupted due to COVID-19 pandemic circumstances
 - Randomized but not completed due to Site Early Termination;
 - Completed double-blind period
 - Patients who had study treatment temporarily interrupted due to COVID-19 pandemic circumstances
- Entered into follow-up period

Statistical Analysis Plan

Sponsor Name: Poxel
Sponsor Protocol ID: PXL065-003

- Discontinued during follow-up period;
 - Patients whose primary reason for withdrawal was due to COVID-19
- Completed follow-up period

In addition, the number and percentage of patients who discontinue early, including a breakdown of the primary reasons for discontinuation from study, will be presented.

A summary of the reasons for screen failure will be produced.

A summary table of randomized patients by site and treatment group will be provided for the randomized set.

A summary table of patients included in each study population (RS, Safety, ITT, PPS) will be produced for the Randomized set and Randomized set with site 065-S . A listing of patients included from each population will be produced, for the Randomized set with site 065-S: .

In addition, a summary table and listing will be produced for discrepancies between the stratification factors in the database and Interactive Web Response System (IWRS).

A listing of IMP kit numbers and assignments will be produced for the Randomized set with site 065-S: .

